5.3.1.3. Overdose

There is no specific experience in the management of ibrutinib overdose in patients. No maximum tolerated dose (MTD) was reached in the Phase 1 study in which subjects received up to 12.5 mg/kg/day (1400 mg/day). Healthy subjects were exposed up to single dose of 1680 mg. One healthy subject experienced reversible Grade 4 hepatic enzyme increases (AST and ALT) after a dose of 1680 mg. Subjects who ingest more than the recommended dosage should be closely monitored and given appropriate supportive treatment.

Refer to Section 11.4 for further information regarding AE reporting.

5.3.1.4. Dose Modification for Adverse Reactions

The dose of ibrutinib should be modified according to the dose modification guidelines in Table 1 if any of the following toxicities occur:

- Grade 4 ANC ($<500/\mu\text{L}$) for more than 7 days. See Section 6.1 for instructions regarding the use of growth factor support.
- Grade 3 thrombocytopenia ($<50,000/\mu\text{L}$) in the presence of clinically significant bleeding events.
- Grade 4 thrombocytopenia ($<25,000/\mu\text{L}$).
- Grade 3 or 4 nausea, vomiting, or diarrhea if persistent, despite optimal anti-emetic and/or anti-diarrheal therapy.
- Any other Grade 4 or unmanageable Grade 3 toxicity.

For Grade 3 or 4 atrial fibrillation or persistent atrial fibrillation of any grade, consider the risks and benefits of ibrutinib treatment. If clinically indicated, the use of anticoagulants or antiplatelet agents may be considered for the thromboprophylaxis of atrial fibrillation (See Section 6.2.4).

If the dose of ibrutinib is reduced, at the investigator's discretion, the dose of ibrutinib may be re-escalated after 2 cycles of a dose reduction in the absence of a recurrence of the toxicity that led to the reduction. Dose changes must be recorded in the Dose Administration eCRF.

Table 1. Ibrutinib Dose Modifications

| Occurrence | Action to be Taken |
|------------|---|
| First | Withhold study drug until recovery to Grade \leq 1 or baseline; may restart at original dose level |
| Second | Withhold study drug until recovery to Grade \leq 1 or baseline; may restart at 1 dose level lower (i.e., 280 mg/day for 420 mg/day dose; 420 mg/day for 560 mg /day dose) |
| Third | Withhold study drug until recovery to Grade \leq 1 or baseline; may restart at 1 dose level lower (i.e., 140 mg/day for 420 mg/day dose; 280 mg/day for 560 mg /day dose) |
| Fourth | Discontinue study drug |

Table 2. Ibrutinib Dose Reduction Levels

| Starting Dose Level | 560 mg |
|------------------------|-------------|
| Dose Reduction Level 1 | 420 mg |
| Dose Reduction Level 2 | 280 mg |
| Dose Reduction Level 3 | Discontinue |
| Dose Reduction Level 4 | NA |
| Dose Reduction Level 5 | NA |

5.3.1.5. Dose Modification for Hepatic Impaired Subjects

Ibrutinib is metabolized in the liver and therefore subjects with clinically significant hepatic impairment at the time of screening (Child-Pugh class B or C) are excluded from study participation. Refer to Appendix 4 for Child-Pugh classification. For subjects with existing chronic mild hepatic impairment (Child-Pugh class A) at enrollment, the starting dose has to be adjusted to a level of 280 mg daily (two capsules). For subjects who develop mild liver impairment while on study (Child-Pugh class A), the recommended dose reduction for ibrutinib is to a level of 280 mg daily (two capsules) unless lower doses had already been implemented. For subjects who develop moderate liver impairment while on study (Child-Pugh class B), the recommended dose reduction is to a level of 140 mg daily (one capsule). Subjects who develop severe hepatic impairment (Child-Pugh class C) must hold study drug until resolved to moderate impairment (Child-Pugh class B) or better and could be re-treated according to resolved hepatic conditions (i.e., 140 mg or 280 mg for moderate or mild impairment, respectively). Subjects who develop acute hepatic toxicity with liver enzymes Grade 3 or higher while on study should be managed per standard dose modification guidelines in Section 5.3.1.4.

5.3.2. Cetuximab

5.3.2.1. Formulation/Packaging/Storage

Commercial supply of cetuximab will be used.

Cetuximab is supplied for intravenous administration at a concentration of 2mg/ml as a 100mg/50ml, single-use vial or as a 200mg/100ml, single-use vial as a sterile, clear, colorless, injectable liquid containing no preservatives. Single-use vials are individually packaged in cartons.

Refer to the pharmacy manual/site investigational product manual for additional guidance on study drug storage, preparation and handling.

Study drug labels will contain information to meet the applicable regulatory requirements.

5.3.2.2. Dose and Administration

Cetuximab is administered intravenously weekly via infusion pump or syringe pump with infusion rate not to exceed 10 mg/min. Patients will be monitored during and after each cetuximab infusion with assessment of vital signs per standard procedure. Premedications will be used as per institutional protocols.

Patients will be monitored for the presence of infusion-related reactions. Dose modification and toxicity management for infusion-related reactions are outlined in the dose modification section (Section 5.3.2.3).

As with any antibody, allergic reactions to dose administration are possible. Appropriate drugs and medical equipment to treat acute anaphylactic reactions must be immediately available, and study personnel must be trained to recognize and treat anaphylaxis. The study site must have immediate access to emergency resuscitation teams and equipment in addition to the ability to admit subjects to an intensive care unit if necessary.

5.3.2.3. Dose Modification for Adverse Reactions

Tables 3 and 4 should be used as guidelines for cetuximab dose modifications. Please refer to the cetuximab label for additional information.

Table 3. Cetuximab Dose Modifications for Infusion Reactions

| NCI-CTCAE Grade | Dose Modification |
|---|---|
| 1 | Reduce infusion rate by 50% |
| 2 | |
| Non-serious grade 3 | |
| Serious grade 3 (e.g. requiring hospitalization) or any grade 4 | Immediately and permanently discontinue cetuximab |

Table 4. Cetuximab Dose Modifications for Dermatologic Toxicity

| Severe Acneiform Rash | Cetuximab Delay/Discontinuation | Outcome | Dose Modification |
|----------------------------|---------------------------------|----------------|--------------------------------------|
| 1 st Occurrence | Delay infusion by 1-2 weeks | Improvement | Continue at 250mg/m ² |
| | | No improvement | Discontinue cetuximab |
| 2 nd Occurrence | Delay infusion by 1-2 weeks | Improvement | Reduce dose to 200 mg/m ² |
| | | No improvement | Discontinue cetuximab |
| 3 rd Occurrence | Delay infusion by 1-2 weeks | Improvement | Reduce dose to 150 mg/m ² |
| | | No improvement | Discontinue cetuximab |
| 4 th Occurrence | Discontinue cetuximab | | |

5.4. Criteria for Permanent Discontinuation of Study Drug

Investigators are encouraged to keep a subject who is experiencing clinical benefit in the study unless significant toxicity puts the subject at risk or routine noncompliance puts the study outcomes at risk. For a complete list of criteria for permanent discontinuation of study treatment, refer to Section 9.2.

An End-of-Treatment Visit (Section 8.3) is required for all subjects except for those subjects who have withdrawn full consent.

6. CONCOMITANT MEDICATIONS/PROCEDURES

Concomitant therapies must be recorded from the time of ICF signing until 30 days after the last dose of study drug.

6.1. Permitted Concomitant Medications

Supportive medications in accordance with standard practice (such as for emesis, diarrhea, etc.) are permitted. Use of neutrophil growth factors (filgrastim and pegfilgrastim) or red blood cell growth factors (erythropoietin) is permitted per institutional policy and in accordance with the ASCO guidelines (Smith 2006). Transfusions may be given in accordance with institutional policy.

Short courses (≤ 14 days) of steroid treatment for non-cancer related medical reasons (e.g., joint inflammation, asthma exacerbation, rash, antiemetic use and infusion reactions) at doses that do not exceed 100mg per day of prednisone or equivalent are permitted. Steroids for management of immune-related adverse events are allowed.

After consultation with the investigator the following may be considered; localized hormonal or bone sparing treatment for non-B-cell malignancies, and localized radiotherapy for medical conditions other than the underlying B-cell malignancies.

The following may be considered: localized hormonal or bone sparing treatment for non-B-cell malignancies, and localized radiotherapy for medical conditions other than the underlying B-cell malignancies.

6.2. Medications to be Used with Caution

6.2.1. CYP3A- Inhibitors/Inducers

Ibrutinib is metabolized primarily by CYP3A. Concomitant use of ibrutinib and drugs that strongly or moderately inhibit CYP3A can increase ibrutinib exposure and therefore strong CYP3A inhibitors should be avoided. If a strong CYP3A inhibitor (e.g., ketoconazole, indinavir, nelfinavir, ritonavir, saquinavir, clarithromycin, telithromycin, itraconazole, nefazadone, cobicistat, and posaconazole) must be used, either reduce ibrutinib dose to 140 mg for the duration of inhibitor use or withhold treatment temporarily (for 7 days or less). Subjects should be monitored for signs of ibrutinib toxicity. If a moderate CYP3A inhibitor (e.g., fluconazole, voriconazole, erythromycin, amprenavir, aprepitant, atazanavir, ciprofloxacin, crizotinib, diltiazem, fosamprenavir, imatinib, verapamil, amiodarone, and dronedarone) must be used, reduce ibrutinib to 140mg (for 840 mg/day dose, reduce to 280 mg) for the duration of the inhibitor use. No dose adjustment is required in combination with mild inhibitors. Avoid grapefruit and Seville oranges during ibrutinib treatment, as these contain moderate inhibitors of CYP3A (see Section 5.3.1.2).

Avoid concomitant use of systemic strong CYP3A inducers (e.g., carbamazepine, rifampin, phenytoin, and St. John's Wort). Consider alternative agents with less CYP3A induction.

A list of common CYP3A inhibitors and inducers is provided in Appendix 3. A comprehensive list of inhibitors, inducers, and substrates may be found at <http://medicine.iupui.edu/clinpharm/ddis/main-table/>. This website is continually revised and should be checked frequently for updates.

For the most comprehensive effect of CYP3A inhibitors or inducers on ibrutinib exposure, please refer to the current version of the IB.

6.2.2. Drugs That May Have Their Plasma Concentrations Altered by Ibrutinib

In vitro studies indicated that ibrutinib is not a substrate of P-glycoprotein (P-gp), but is a mild inhibitor (with an IC₅₀ of 2.15 µg/mL). Ibrutinib is not expected to have systemic drug-drug interactions with P-gp substrates. However, it cannot be excluded that ibrutinib could inhibit intestinal P-gp and BCRP after a therapeutic dose. There is no clinical data available; therefore,

to avoid a potential interaction in the GI tract, narrow therapeutic range P-gp substrates such as digoxin or methotrexate, should be taken at least 6 hours before or after ibrutinib.

6.2.3. QT Prolonging Agents

Any medications known to cause QT prolongation should be used with caution; periodic electrocardiogram (ECG) and electrolyte monitoring should be considered.

6.2.4. Antiplatelet Agents and Anticoagulants

Warfarin or vitamin K antagonists should not be administered concomitantly with ibrutinib. Supplements such as fish oil and vitamin E preparations should be avoided. Use ibrutinib with caution in subjects requiring other anticoagulants or medications that inhibit platelet function. In an in vitro platelet function study, inhibitory effects of ibrutinib on collagen induced platelet aggregation were observed. Supplements such as fish oil and vitamin E preparations should be avoided during treatment with ibrutinib. Bleeding events of any grade, including bruising and petechiae, occurred in subjects treated with ibrutinib. Ibrutinib should be held at least 3 to 7 days pre- and post-surgery depending upon the type of surgery and the risk of bleeding (see Section 6.4). Subjects with congenital bleeding diathesis have not been studied.

Subjects requiring the initiation of therapeutic anticoagulation therapy (e.g., atrial fibrillation), consider the risks and benefits of continuing ibrutinib treatment. If therapeutic anticoagulation is clinically indicated, treatment with ibrutinib should be held and not be restarted until the subject is clinically stable and has no signs of bleeding. Subjects should be observed closely for signs and symptoms of bleeding. No dose reduction is required when study drug is restarted.

6.3. Prohibited Concomitant Medications

Any non-study protocol related chemotherapy, anticancer immunotherapy, experimental therapy, or radiotherapy are prohibited while the subject is receiving ibrutinib treatment.

Corticosteroids for the treatment of the underlying malignancy is prohibited (Refer to Section 6.1 for further guidance).

6.4. Guidelines for Ibrutinib Management with Surgeries or Procedure

Ibrutinib may increase risk of bleeding with invasive procedures or surgery. The following guidance should be applied to the use of ibrutinib in the perioperative period for subjects who require surgical intervention or an invasive procedure while receiving ibrutinib:

6.4.1. Minor Surgical Procedures

For minor procedures (such as a central line placement, skin or needle biopsy, lumbar puncture [other than shunt reservoir access], thoracentesis, or paracentesis) ibrutinib should be held for at least 3 days prior to the procedure and should not be restarted for at least 3 days after the

procedure. For bone marrow biopsies that are performed while the subject is on ibrutinib, it is not necessary to hold ibrutinib for these procedures.

6.4.2. Major Surgical Procedures

For any surgery or invasive procedure requiring sutures or staples for closure, ibrutinib should be held at least 7 days prior to the intervention (except for emergency procedures) and should be held at least 7 days after the procedure and restarted at the discretion of the investigator when the surgical site is reasonably healed without serosanguineous drainage or the need for drainage tubes.

7. STUDY EVALUATIONS

7.1. Description of Procedures

7.1.1. Assessments

1. Informed consent
2. Medical history – Complete medical, surgical, and oncologic history. Changes from screening [e.g., worsening severity or abnormal findings) are considered to be adverse events (AEs)].
3. Demographics – Profile will include date of birth, gender, race, and ethnicity.
4. Review patient eligibility criteria – Review eligibility criteria as described in Section 4 to ensure patient qualification for study entry.
5. Review previous and concomitant medications – All prior medication taken by the patient within 4 weeks before starting the study is to be recoded. Concomitant medications taken by the patient during the study are to be recorded up until 30 days after last study dose. If a reportable AE (see Section 11.4) occurs within 30 days after last study dose, recording of concomitant medications should continue until resolution of the adverse event.
6. Physical exam including vital signs, height, body weight, and pulse oximetry. Physical exam to include thorough examination of the oral cavity and neck.
7. ECOG performance status evaluated at screening and monthly intervals.
8. Adverse event assessment – Baseline assessment of patient status for determining adverse events, that is, change from

baseline. See Section 11.4 for Adverse Event monitoring and reporting.

9. Twelve lead ECG at baseline and when clinically indicated

7.1.2. Laboratory

1. Hematology – Complete blood count with differential
2. Screening coagulation studies – International normalized ratio (INR), protime (PT), activated partial thromboplastin time (aPTT)
3. Serum chemistries – Electrolytes (sodium, potassium, chloride, bicarbonate), BUN, creatinine, random glucose, calcium, magnesium, albumin, ALT/SGPT, AST/SGOT, total bilirubin, total protein, magnesium
4. Hepatitis B and C serologies – Hepatitis B surface antigen, hepatitis B surface antibody, hepatitis B core antibody total, hepatitis C antibody
5. HIV serology – HIV 1/2 antibody
6. Pregnancy test for females of child bearing potential – Serum beta-hCG.
7. Blood draw for correlative testing – 30 mL of peripheral blood will be collected prior to initiation of study treatment and on cycle 2 day 1 (+/- 7 days)

7.1.3. Diagnostics/Procedures

1. CT scan of the soft tissue neck and thorax with intravenous contrast for baseline disease assessment. Additional scans (e.g., abdomen/pelvis etc.) may be conducted as needed per each patient's disease burden.
2. Tumor biopsy for correlative testing – A tumor biopsy sample will be collected prior to initiation of study treatment (unless previously archived but new sample preferred) and on cycle 2 day 1 (+/- 7 days)

7.1.4. Pharmacokinetics/Biomarkers (as applicable)

1. Blood and tumor tissue specimens prior to initiation of study treatment and on cycle 2 day 1 (+/- 7 days) to measure potential biomarkers that can be used to predict response to therapy for an individual patient in future trials.

7.2.Efficacy Evaluations

1. Restaging CT scans will be performed after every 2 cycles and compared to baseline to assess clinical response to study treatment. Response will be determined based on RECIST 1.1 criteria (see section 10).

7.3.Sample Collection and Handling

Blood and tumor tissue specimens will be collected prior to initiation of study treatment and on cycle 2 day 1 (+/- 7 days). These specimens will be collected as part of this protocol and stored in the tissue bank.

Additional peripheral blood and tumor tissue samples may be collected on patients who relapse/progress while in follow-up as part of this protocol. The samples in follow-up are optional.

These samples will be delivered to the tissue procurement core facility at each designated cancer center and processed according to institutional standard operating procedures and frozen.

8. STUDY PROCEDURES

8.1.Screening Phase

The following screening procedures listed will be conducted within 4 weeks prior to initiation and pick-up of ibrutinib. Routine tests or evaluations taken prior to patient consent may be used to satisfy entry criteria.

1. Obtain signed, written informed consent – consent must be obtained prior to initiation of ibrutinib in order to obtain appropriate study lab samples
2. Demography
3. Medical history
4. Concomitant medications, including parenteral nutrition: record all medications from the start of ibrutinib
5. Physical examination, including vital signs, height, body weight, and pulse oximetry
6. Documented confirmation of disease and staging
7. ECOG performance status assessment (see Appendix 2)
8. Baseline CT imaging to quantify disease burden per RECIST criteria v1.1
9. Clinical laboratory testing: CBC and differential, comprehensive metabolic panel (CMP), screening coagulation studies, pregnancy test for women of child bearing potential (within 72 hours of starting ibrutinib), HIV serology, hepatitis B and C serologies with confirmatory negative PCR testing if serologies are positive
10. Tumor biopsy for specimen analysis and correlative testing or confirmation of previously archived specimen
11. HPV and/or p16 tumor status by institutional standard procedures

12. Verify that patient meets all entry criteria
13. ECG

8.2.Treatment Phase

For this study, the following assessments will be performed on Cycle 1, Day 8 (+/- 3 days) of the second agent of each study treatment:

1. Brief update of medical history
2. Physical exam with vital signs, height, body weight, and pulse oximetry
3. Document concomitant medications
4. Collect adverse events
5. Labs: CBC with differential, CMP, magnesium
6. ECOG performance assessment

The following assessments will be performed on a monthly basis, coinciding with Day 1 of each subsequent cycle (+/- 3 days).

1. Brief update of medical history
2. Physical exam with vital signs, height, body weight, and pulse oximetry
3. Document concomitant medications
4. Collect adverse events
5. Labs: CBC with differential, CMP, magnesium
6. ECOG performance status assessment
7. Tumor tissue biopsy for specimen analysis and correlative testing and blood draw for correlative studies around Day 28 of cycle 1 only (+/- 7 days)

The following assessments will be performed on day 15 of each cycle (+/- 3 days), prior to cetuximab infusion:

1. Labs: CMP, magnesium

8.3.Follow-up Phase

Patients will be followed for 5 years from study entry, or until death, whichever occurs first. Patients removed from study for unacceptable adverse events will be followed until resolution or stabilization of the adverse event. Patients taken off study to undergo non-study treatment will be censored as progressive disease as of the date they begin non-protocol therapy. Patients refusing protocol-defined follow-up will be censored as to their status on the day of last contact.

Patients will be seen within 28 days of the last treatment dose. At this visit, the following assessments will be conducted:

1. Brief update of medical history
2. Physical exam with vital signs, height, body weight, and pulse oximetry
3. Labs: CBC with differential, basic metabolic panel, hepatic function panel
4. ECOG performance status assessment

5. Collect adverse events

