5.1.1. Route and schedule

In this study, ibrutinib administration will begin 7 days prior to the start of the second agent as supported by preclinical studies.

Ibrutinib will be administered continuously at 560mg given as 4 capsules on a daily basis of each 28 day cycle. On days where patients receive both ibrutinib and the second agent (cetuximab), ibrutinib will be given first. Ibrutinib will be administered per institutional guidelines.

Cetuximab will be administered at 400mg/m² x 1 as a loading dose given as a 120 minute IV infusion, following by 250 mg/m² weekly. Subsequent infusions may be given over 60 minutes. Cetuximab will be administered per institutional guidelines.

5.2.Dose Modifications

Please see sections 5.4.1.4, 5.4.2.2, and 5.4.3.2 for discussion of dose modifications for ibrutinib and cetuximab for toxicities. If one drug is held, the other drug may be continued. For example, if a patient develops neutropenia thought to be related to ibrutinib or cetuximab may be continued. If cetuximab is held for toxicities clearly related to those drugs, ibrutinib treatment may continue. When there are toxicities that may be attributed to either agent (e.g., diarrhea), a discussion will occur between the treating physician and the study principal investigator to determine whether one drug or both should be held.

5.3.Study Medication

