12.6. Safety Analysis

Safety will be evaluated according to the CTCAE v4.0. Safety assessments will be based on medical review of adverse event reports and the results of vital sign measurements, physical examinations, and clinical laboratory tests throughout the conduct of the study. Laboratory test abnormalities will be reviewed for clinical significance and only those deemed clinically significant will be reported as adverse events. The MedDRA medical dictionary will be used to map the AE/SAE verbatim terms to specific system organ classes and preferred terms. Frequencies and incidence rates of AEs and SAEs will be tabulated and presented in by-subject listings by system organ classes and preferred term. Summary tables of AEs by grade and body system will be presented.

All adverse events of any grade occurring in the first 48 hours following combinatorial treatment administration will also be assessed as potential infusion reactions. The number and percent of subjects who develop any adverse event consistent with an infusion reaction will be summarized by overall grade.

Early stopping for safety: Data safety and toxicity will be continuously monitored in the study under the guidance from the Data Safety Monitoring Committee. The study will be suspended if there are 1 or more treatment-related deaths within the first 6 patients enrolled during the initial safety assessment, which indicates the treatment-related mortality is $> 5\%$. These treatment-

related deaths must be attributable to direct organ toxicity by study treatment agents with the exception of deaths attributable to immunosuppression (i.e. infections).

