Appendix 1. Schedule of Assessments

SCHEDULE OF ASSESSMENTS

| Procedure | Screen/ Baseline (≤ 28 days, unless otherwise noted) | Treatment Cycles (4-week cycles) | | | | | | | | | | | | | | | | | | | | End of Treatment (within 28 days after last dose) | Follow-up (q2 months (± 14 days) from EOT) | |
|---------------------------------------|---|----------------------------------|---|---|----|----|-----------------------|---|----|----|-----------------------|---|----|----|-----------------------|---|----|----|--|---|----|---|---|----|
| | | Cycle 1 (± 3 days) | | | | | Cycle 2 (± 3 days) | | | | Cycle 3 (± 3 days) | | | | Cycle 4 (± 3 days) | | | | Each Additional Cycle (± 3 days) | | | | | |
| | | -7 | 1 | 8 | 15 | 22 | 1 | 8 | 15 | 22 | 1 | 8 | 15 | 22 | 1 | 8 | 15 | 22 | 1 | 8 | 15 | | | 22 |
| Informed Consent | X | | | | | | | | | | | | | | | | | | | | | | | |
| Eligibility | X | | | | | | | | | | | | | | | | | | | | | | | |
| Medical History | X | | | | | | | | | | | | | | | | | | | | | | | |
| HPV or p16 status ¹ | | | | | | | | | | | | | | | | | | | | | | | | |
| Demographics | X | | | | | | | | | | | | | | | | | | | | | | | |
| Concomitant Medications Assessment | X | | | X | | | X | | | | X | | | | X | | | | X | | | | X | |
| Adverse Event Assessment | X | | | X | | | X | | | | X | | | | X | | | | X | | | | X | |
| Physical Exam ² | X | | | X | | | X | | | | X | | | | X | | | | X | | | | X | |
| Vital Signs & Height | X | | | X | | | X | | | | X | | | | X | | | | X | | | | X | |
| ECOG | X | | | X | | | X | | | | X | | | | X | | | | X | | | | X | |
| CBC with Diff ³ | X | X | | X | | | X | | | | X | | | | X | | | | X | | | | X | |
| CMP and magnesium ⁴ | X | X | | X | x | | X | | x | | X | | x | | X | | x | | X | | x | | X | |
| PT/INR, aPTT | X | X | | | | | | | | | | | | | | | | | | | | | | |
| Pregnancy test ⁵ | Within 72 hours | | | | | | | | | | | | | | | | | | | | | | | |
| HIV | X | | | | | | | | | | | | | | | | | | | | | | | |
| HEP B & C | X | | | | | | | | | | | | | | | | | | | | | | | |
| T4 and TSH | X | | | | | | X | | | | X | | | | X | | | | X | | | | | |
| ECG | X | | | | | | | | | | | | | | | | | | | | | | | |
| Tumor tissue collection ⁶ | Within 42 days | | | | | | X ¹ 0 | | | | | | | | | | | | | | | | | |

[illegible]

Cycles are 28 days in length, with the exception of cycle 1, which is 35 days long due to start of ibrutinib 7 days prior to second drug.

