Appendix 5. Patient Pill Diaries

Participant Dosing Diary and Instructions

Study IRB #161755 **Study site and ID # _____**
Cycle #: _____

Site Staff Instructions:

Please enter below the dates (mm/dd/yyyy) for the current cycle for Day 1-28.

| | Study Medication | | Daily Dose | Source |
|---|---|--|-----------------------|---------------|
| Day 1 - 28 Medications From: -- / / -- (MM / DD / YYYY) To: -- / / -- (MM / DD / YYYY) |  | 140 mg Ibrutinib x 4 capsules = 560 mg daily | 4 capsules | 140 mg bottle |

Participant Instructions:

- Swallow study drug whole and do not to chew or open them prior to swallowing.
- Take medication four capsules per day WITH 8 OZ OF WATER, at approximately the same time daily.
- If you miss a day's dose at the scheduled time, it can be taken as soon as possible on same day with a return to the normal schedule the following day.
- If you miss a day's dose entirely, you should NOT make it up the next day.
- If you vomit after taking a dose you should NOT make it up and should resume treatment the next day.
- If you inadvertently take 1 extra dose during a day, you should NOT take the next day's dose.
- Keep the medication in the bottles provided and do not transfer it to any other container.
- Record each dose of study medication in the diary section below. To prevent any dosage error, the participant diary should be completed every day.
- UNUSED DRUG and bottles should be RETURNED to the site at the next study visit.
- ALWAYS BRING your completed participant diary to the clinic at EACH study visit.
- Please avoid grapefruit and Seville oranges for the duration of the study.
- Please avoid using CYP3A inhibitors/inducers (e.g. indinavir, nefazodone)
- In case of any question, problem, or if you are not feeling well, please contact your study doctor.

| DAY | DATE (mm/dd/yy) | TIME Hour/Min (24:00 clock) | Number of Capsules TAKEN (Daily dose is 4 capsules, please add to the appropriate columns below; "4" if 4 pills were taken or "0" if no pills were taken) | COMMENT (e.g., Please use this section to write down any side effects you are experiencing on a given day, explanation for any extra doses taken or missed doses, etc.) |
|---|--------------------|-----------------------------------|---|---|
| | | | 140 mg = each pill | |
| 1 | | | | |
| The dose of Day 1 should be taken in the clinic according to site staff's instructions. Take Ibrutinib before Cetuximab infusion. | | | | |
| 2 | | | | |
| 3 | | | | |
| 4 | | | | |

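### No adverse event review is scheduled from the first ibrutinib dose until Cycle 1 Day 8, so ibrutinib-alone events are first asked about after cetuximab has started and are not tabulated separately

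*Combined protocol and SAP*

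**What the plan says.** Section 5.1.1 sets the lead-in: "ibrutinib administration will begin 7 days prior to the start of the second agent as supported by preclinical studies". Appendix 1 confirms it in a note that cycles last 28 days "with the exception of cycle 1, which is 35 days long due to start of ibrutinib 7 days prior to second drug".

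Section 8.2 names the on-treatment occasions for collecting adverse events. The first is Day 8 of cetuximab: "the following assessments will be performed on Cycle 1, Day 8 (+/- 3 days) of the second agent". The later ones are monthly: "The following assessments will be performed on a monthly basis, coinciding with Day 1 of each subsequent cycle (+/- 3 days". A third list, introduced by "The following assessments will be performed on day 15 of each cycle (+/- 3 days), prior to cetuximab infusion", contains laboratory tests only.

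The Appendix 1 row agrees: "Adverse Event Assessment | X | | | X | | | X". Read against the column heads, it has a mark at screening, blanks at Day -7 and Cycle 1 Day 1, a mark at Day 8, blanks at Days 15 and 22, and then a mark at Day 1 of Cycle 2. Later cycles are marked on Day 1 only, with a final mark at end of treatment.

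Section 13.4.1 has a different rule: investigators assess adverse events whenever a subject is evaluated, and each event is recorded with start and end dates. Section 13.4.2 captures all events from signed consent to 30 days after the last dose.

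Section 12.6 contains the analysis rule: "All adverse events of any grade occurring in the first 48 hours following combinatorial treatment administration will also be assessed as potential infusion reactions". It then summarises the subjects whose events are consistent with such a reaction. It plans no split by treatment period.

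**The concern.** The lead-in is the only time when a patient takes ibrutinib without cetuximab, so it is the cleanest evidence on which drug caused an event. The two drugs overlap: rash is described for both (Sections 1.5.1.8 and 1.5.3.4), and Section 5.2 uses diarrhea as its example of an event that either could cause. Section 5.2 also makes the decision to hold one drug or both depend on attribution. Onset relative to the first cetuximab infusion is therefore a working piece of information.

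Nobody is scheduled to ask at the point where the lead-in ends. The first infusion also matters most for reactions: Section 1.5.3.1 puts about 90% of severe infusion reactions there. Yet there is no adverse event baseline taken just before it against which the 48-hour events can be judged.

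Frequency and severity of adverse events is a secondary objective (Section 2.2.1). With 18 patients, one patient classified differently moves a rate by 1/18, or 5.6 percentage points.

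**Working it through.** The plan states no figure on this point, so there is none to reproduce. The check is a calendar count.

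**Inputs.** First ibrutinib is t = 0 and first cetuximab (Cycle 1 Day 1) is t = 7 (Section 5.1.1). Cetuximab is weekly, so infusions fall on Days 1, 8, 15 and 22 of each 28-day cycle (Sections 3.2.2 and 5.3.2.2). Scheduled reviews fall on Cycle 1 Day 8 and on Day 1 of each later cycle, each within 3 days either way (Section 8.2).

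**First dose to first review.** Cycle 1 Day 8 is t = 7 + 7 = 14 days. With the window this is 14 - 3 = 11 to 14 + 3 = 17 days. That spans the whole 7-day lead-in and about a week of the combination.

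**Age of the last review at first cetuximab.** Screening may be up to 28 days before ibrutinib (Section 8.1, Appendix 1), so it can be 28 + 7 = 35 days old.

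**Diary.** Cycle 1 lasts 35 days and the diary has rows for Days 1 to 28, leaving 35 - 28 = 7 days without rows. These are the lead-in days, because diary Day 1 is a cetuximab day: "The dose of Day 1 should be taken in the clinic", and the same entry tells the patient to take ibrutinib before the infusion.

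**Days from each infusion to the next scheduled review**, taking a same-day review as done before the infusion. The last two columns show what happens if the scheduled Day 15 laboratory visit also counts as an evaluation under Section 13.4.1.

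| Infusion | Cycle 1 | Cycle 2 on | Cycle 1, Day 15 counted | Cycle 2 on, Day 15 counted |
|---|---|---|---|---|
| Day 1 | 7 | 28 | 7 | 14 |
| Day 8 | 21 | 21 | 7 | 7 |
| Day 15 | 14 | 14 | 14 | 14 |
| Day 22 | 7 | 7 | 7 | 7 |

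At nominal dates, 0 of 16 infusions over four cycles are followed by a scheduled review within 48 hours. From Cycle 2 there is one review per four infusions.

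**The two rules side by side.** Section 8.2 and Appendix 1 name Day 8 of Cycle 1 and Day 1 of later cycles. Section 13.4.1 names every evaluation and does not define which visits count. A site could follow either, and the gaps differ by up to 28 - 14 = 14 days according to the choice.

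**The case against.** The plan has real safeguards. All events are captured from consent, with start dates, so an event that began in the lead-in can be placed there at analysis. Section 5.3.2.2 requires monitoring during and after every infusion. The diary in Appendix 5 is to be filled in daily, has a column for side effects on the day, covers all four infusion days and is brought to each visit. Serious events are reported within 24 hours (Section 13.4.6), whatever the visit schedule. When either drug may be the cause, Section 5.2 requires a discussion with the study principal investigator.

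All of this stands, and it defeats three stronger conclusions that a reader might infer.

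- *Lead-in toxicity is lost in the combination.* The documents do not support this, because start dates allow separation. What remains is late questioning, no diary rows for that week, and no planned table.
- *The 48-hour count rests on recall.* In-clinic reactions are observed and later symptoms have a same-day diary column. Recall matters only for events after discharge that the patient did not write down. Nor is an event that began earlier counted automatically: Section 12.6 treats 48-hour events as potential reactions and summarises those consistent with one.
- *The recorded reaction rate must fall with time on drug.* The gaps do not show that. Only the Day 1 gap changes, once, from 7 to 28 days. After that every cycle is the same.

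The safeguards leave one thing open. Capture periods and start dates say what must be recorded, not when someone asks. For the lead-in week neither the diary nor a scheduled review does the asking.

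**Conclusion.** The point holds as a gap in scheduling and tabulation. Section 8.2 and Appendix 1 agree with each other, so this is not an effect of a broken table. The first scheduled review comes 14 days (11 to 17) after the first ibrutinib dose, with no review before the first cetuximab infusion, no diary rows for the lead-in and no by-onset table. From Cycle 2 the schedule gives one review per four infusions, which needs reconciling with Section 13.4.1.

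The loss is limited to lead-in events and to unrecorded events after discharge. The documents do not allow an estimate of how many events that is. The count of 0 in 16 assumes nominal dates and a review before any same-day infusion. If the review followed the infusion, the Day 8 infusion of Cycle 1 and the Day 1 infusion of each later cycle would have a same-day review.

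No decision rule is affected. The primary endpoint is response, and the safety suspension rule counts treatment-related deaths. The change is worth making because it is cheap and improves the attribution on which Section 5.2 relies.

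**What to change.** 1. In Section 8.2 and Appendix 1, mark adverse event assessment at Cycle 1 Day 1, before the first cetuximab infusion, and at the existing weekly infusion visits (Days 1, 8, 15 and 22). This brings both places into line with Section 13.4.1.
2. In Appendix 5, add diary rows for the 7 lead-in days.
3. In Section 12.6, tabulate events by onset: from first ibrutinib to just before first cetuximab, and from first cetuximab onward. State that an event already present before an infusion and not worsened after it is left out of the 48-hour infusion-reaction count.

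The cost is a short query at visits that already take place, a few more case report form entries and one extra table. No visit or procedure is added.
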